### **17.1.28 INTERACTION WITH PACEMAKER/CRT/ICD LEAD**

- Lead Dislodgement: Radiographic, micro dislodgement, electrical or electrocardiographic evidence of electrode displacement from the original implant site or electrode displacement that adversely affects pacing and/or lead performance
- Failure to Sense/Undersensing (Cardiac): Intermittent or complete loss of sensing or failure to detect the intended intrinsic cardiac signals (atrial or ventricular) during non-blanking periods at programmed sensitivity settings.
- Failure to Capture (Cardiac):
  - Intermittent: Intermittent or irregular failure to achieve cardiac stimulation (atrial or ventricular) at programmed output delivered outside of the cardiac refractory period at settings previously effective
  - Sustained: Continuous failure to stimulate the heart with stimuli delivered outside of the cardiac refractory period at programmed setting previously effective
  - Lead Fracture: Visual, electrical, and/or radiographic evidence of mechanical break within the lead conductor (includes connectors, coils and/or electrodes)
  - Failure to Pace: lack of the pacer electrical output once the heart rate is below the programmed lower rate of the pacemaker.

### **17.1.29 MITRAL REGURGITATION**

Mitral regurgitation will be classified according to the Recommendations for Noninvasive Evaluation of Native Valvular Regurgitation: A report from the American Society of Echocardiography developed in Collaboration with the Society of Cardiovascular Magnetic Resonance; JASE, 2017(11).

Qualitative and Quantitative Parameters useful in Grading Mitral Regurgitation Severity			
MR Severity*			
	Mild	Moderate	Severe
Structural Parameters			

# The Early Feasibility Study of the Intrepid™ TMVR Transseptal System Clinical Investigation Plan

Version 4.0

Page 89 of 102

Medtronic

Qualitative and Quantitative Parameters useful in Grading Mitral Regurgitation Severity			
MR Severity*			
	Mild	Moderate	Severe
MV morphology	None or mild leaflet thickening (e.g., mild thickening, calcifications or prolapse, mild tenting)	Moderate leaflet abnormality of moderate tenting	Severe valve lesions (primary: flail leaflet, ruptured papillary muscle, severe retraction, large perforation; secondary: severe tenting, poor leaflet coaptation)
LV and LA size†	Usually normal	Normal or mild dilated	Dilated‡
Qualitative Doppler			
Color flow jet area§	Small, central, narrow, often brief	Variable	Large central jet (>50% of LA) or eccentric wall-impinging jet of variable size
Flow convergence¶	Not visible, transient or small	Intermediate in size and duration	Large throughout systole
CWD jet	Faint/partial/parabolic	Dense but partial or parabolic	Holosystolic/dense/triangular
Semiquantitative			
VCW(cm)	<0.3	Intermediate	≥ 0.7 (>0.8 for biplane)¶
Pulmonary vein flow#	Systolic dominance (may be blunted in LV dysfunction or AF)	Normal or systolic blunting#	Systolic flow reversal†
Mitral inflow**	A-wave dominant	Variable	E-wave dominant (>1.2 m/sec)
Quantitative††,‡‡			
EROA, 2D PISA (cm  )	<0.20	0.20-0.29      0.30-0.39	≥ 0.40 (may be lower in secondary MR with elliptical ROA)
RVol (mL)	<30	30-44      45-59††	≥ 60 (may be lower in low flow conditions)
RF (%)	<30	30-39      40-49	≥ 50

Medtronic Business Restricted

**CONFIDENTIAL**

056-F275, vC Clinical Investigation Plan Template

# The Early Feasibility Study of the Intrepid™ TMVR Transseptal System Clinical Investigation Plan

Version 4.0

Page 90 of 102

Medtronic

## Qualitative and Quantitative Parameters useful in Grading Mitral Regurgitation Severity

### MR Severity\*

	Mild	Moderate	Severe
ROA, Regurgitant orifice area.			
Bolded qualitative and semiquantitative signs are considered specific for their MR grade.			
* All parameters have limitations, and an integrated approach must be used that weighs the strength of each echocardiographic measurement. All signs and measures should be interpreted in an individualized manner that accounts for body size, sex, and all other patient characteristics.			
† This pertains mostly to patients with primary MR.			
‡ LV and LA can be within the “normal” range for patients with acute severe MR or with chronic severe MR who have small body size, particularly women, or with small LV size preceding the occurrence of MR			
§ With Nyquist limit 50-70 cm/sec.			
" Small flow convergence is usually <0.3 cm, and large is \$ 1 cm at a Nyquist limit of 30-40 cm/sec.			
¶ For average between apical two- and four-chamber views			
# Influenced by many other factors (LV diastolic function, atrial fibrillation, LA pressure).			
** Most valid in patients >50 years old and is influenced by other causes of elevated LA pressure.			
†† Discrepancies among EROA, RF, and RVol may arise in the setting of low or high flow states.			
‡‡ Quantitative parameters can help subclassify the moderate regurgitation group.			

### 17.1.30 MITRAL STENOSIS

Mitral stenosis will be classified according to the 2008 Focused Update Incorporated into the ACC/AHA 2006 Guidelines for the Management of Patients with Valvular Heart Disease; JACC, 2008 (12).

Mitral Stenosis			
Indicator	Mild	Moderate	Severe
Mean gradient (mmHg)*	Less than 5	5–10	Greater than 10
Pulmonary artery systolic pressure (mmHg)	Less than 30	30–50	Greater than 50
Valve area (cm  )	Greater than 1.5	1.0–1.5	Less than 1.0

\* Valve gradients are flow dependent and when used as estimates of severity of valve stenosis should be assessed with knowledge of cardiac output or forward flow across the valve. Modified from the Journal of the American Society of Echocardiography, 16, Zoghbi WA, Recommendations for evaluation of the severity of native valvular regurgitation with two-dimensional and Doppler echocardiography, 777–802, Copyright 2003, with permission from American Society of Echocardiography.

Medtronic Business Restricted

CONFIDENTIAL

056-F275, vC Clinical Investigation Plan Template

### **17.1.31 MITRAL VALVE DYSFUNCTION**

Mitral valve dysfunction will be classified according to the Mitral Valve Academic Research Consortium (MVARC); Clinical Trial Design Principles and Endpoint Definitions for Transcatheter Mitral Valve Repair and Replacement: Part 2: Endpoint Definitions; JACC, 2015 (14).

The device performs as intended without complication but does not adequately reduce the degree of MR (MR > moderate [2+], or fails to relieve or creates new mitral stenosis [EROA <1.5 cm^2 or transmitral gradient  $\geq$ 5 mm Hg]).

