# The Early Feasibility Study of the Intrepid™ TMVR Transseptal System Clinical Investigation Plan

Version 4.0

Page 7 of 102

Medtronic

Term	Definition
EROA	Effective Regurgitant Orifice Area
FAL	Foreseeable Adverse Event List
FD	Financial Disclosure
FDA	Food and Drug Administration
FDAAA	Food and Drug Administration Amendments Act
FEV1	Forced Expiratory Volume
GCP	Good Clinical Practice
GDPR	General Data Protection Regulation
GI	Gastrointestinal
HIPAA	Health Insurance Portability and Accountability Act
IB	Investigator Brochure
IC/ICF	Informed Consent/Informed Consent Form
ICD	Implantable Cardiac Defibrillator
ICH	International Conference of Harmonization
ICU	Intensive Care Unit
IDE	Investigational Device Exemption
IFU	Instructions For Use
ICU	Intensive Care Unit
INR	International Normalized Ratio
IPG	Implantable Pulse Generator
IRB	Institutional Review Board
IVC	Inferior Vena Cava
KCCQ	Kansas City Cardiomyopathy Questionnaire
LV	Left Ventricle
LVAD	Left Ventricular Assist Device
LVEDD	Left Ventricular End Diastolic Diameter
LVEDV	Left Ventricular End Diastolic Volume
LVEF	Left Ventricular Ejection Fraction
LVOT	Left Ventricular Outflow Tract
MDCT	Multi-Dimensional Computed Tomography
MDD	Medical Device Directive
MedDRA	Medical Dictionary for Regulatory Activities
MHLW	Ministry of Health, Labour, and Welfare

Medtronic Business Restricted

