#### **4.2.2 Secondary Performance Endpoints**

- Successful access, delivery of implant, and retrieval of the delivery system
- Reduction in MR Grade from baseline (measured by echo through 30 days post-procedure)
- No significant MV stenosis (measured by echo through 30 days post-procedure)
- LV outflow tract (LVOT) patency (measured by echo through 30 days post-procedure)
- Change in NYHA Class from baseline (through 30 days post-procedure)

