## **Appendix B: Participant Information and Consent Form**

## **Appendix C: Instructions for Use**

## Appendix D: Endpoint Definitions

Analysis of study results will include the following additional MVARC defined exploratory endpoints:

**Technical Success** (measures at exit from catheterization laboratory)

All of the following must be present:

- I. Absence of procedural mortality; and
- II. Successful access, delivery, and retrieval of the device delivery system; and
- III. Successful deployment and correct positioning of the first intended device; and
- IV. Freedom from emergency surgery or reintervention related to the device or access procedure

**Device Success** (measured at 30 days and at all later post-procedural intervals):

All of the following must be present:

- I. Absence of procedural mortality or stroke; and
- II. Proper placement and positioning of the device; and
- III. Freedom from unplanned surgical or interventional procedures related to the device or access procedure; and
- IV. Continued intended safety and performance of the device, including:
  - a. No evidence of structural or functional failure
  - b. No specific device-related technical failure issues and complications
  - c. Reduction of MR to either optimal or acceptable levels without significant mitral stenosis (i.e., post-procedure EROA is 1.5 cm^2 with a transmural gradient <5 mm Hg), and with no greater than mild (1+) paravalvular MR (and without associated hemolysis)

**Procedural Success** (measured at 30 days)

All of the following must be present:

- I. Device success (either optimal or acceptable), and
- II. Absence of major device or procedure related serious adverse event, including:
  - a. Death
  - b. Stroke
  - c. Life-threatening bleeding (MVARC scale)
  - d. Major vascular complications
  - e. Major cardiac structural complications
  - f. Stage 2 or 3 acute kidney injury (includes new dialysis)
  - g. Myocardial infarction or coronary ischemia requiring PCI or CABG
  - h. Severe hypotension, heart failure, or respiratory failure requiring intravenous pressors or invasive or mechanical heart failure treatments such as ultrafiltration or hemodynamic assist devices, including intra-aortic balloon pumps or left ventricular or biventricular assist devices, or prolonged intubation for 48 h
  - i. Any valve-related dysfunction, migration, thrombosis, or other complication requiring surgery or repeat intervention

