#### Endpoint Definition/Parameters to Be Estimated:

This endpoint is defined using variables on the core lab echo CRF.

No significant MV stenosis will be assessed by 2 definitions:

- 1) A MV mean gradient  $< 5$  mmHg and effective orifice area (EOA)  $\geq 1.5 \text{ cm}^2$  based on echocardiography core lab data.
- 2) A MV mean gradient  $< 10$  mmHg.

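### EFS CIP 17.1.31 sets the stenosis limb of mitral valve dysfunction on EROA, a regurgitant area, so read literally the limb cannot discriminate between valves

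*Combined protocol and SAP*

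**What the plan says.** **EFS CIP 17.1.31 (Mitral Valve Dysfunction).** This event definition, attributed to MVARC, has two limbs joined by *or*. One is residual MR above moderate. The other is that the device "fails to relieve or creates new mitral stenosis [EROA <1.5 cm"² or gives a transmitral gradient of at least 5 mm Hg.

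**EFS CIP 1.0 (Glossary).** EROA is expanded as "Effective Regurgitant Orifice Area". EOA is not listed.

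**EFS CIP 17.1.29 (Mitral Regurgitation).** The grading table uses EROA as a measure of leak: below 0.20 cm² is mild, and the severe entry is "≥ 0.40 (may be lower in secondary MR with elliptical ROA"). The severe entry for regurgitant volume, in mL, is "≥ 60 (may be lower in low flow conditions").

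**EFS CIP 17.1.30 (Mitral Stenosis).** "Mitral stenosis will be classified according to the 2008 Focused Update" of the ACC/AHA guidelines. It uses mean gradient, pulmonary artery systolic pressure and valve area, and does not mention EROA.

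**EFS CIP 4.2.2.** A secondary endpoint is "No significant MV stenosis (measured by echo through 30 days post-procedure"). No numeric criterion is given and neither appendix section is cited.

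**Pilot CIP-1403, Appendix D (Device Success, item IV.c).** Absence of significant stenosis is explained by "post-procedure EROA is 1.5 cm"² together with a gradient below 5 mm Hg.

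**Pilot SAP 7.9.2 and 7.9.3.** Definition 1 of the stenosis endpoint requires a mean gradient below 5 mmHg and an "effective orifice area (EOA") of at least 1.5 cm². Device success in 7.9.3 uses the same EOA cut-off.

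**The concern.** Stenosis is restricted forward flow, and a small forward orifice is the abnormal finding. Regurgitant orifice area runs the other way: a small value is good and zero is ideal. Placing a regurgitant area in a rule that flags small values makes a competent valve meet the criterion for stenosis.

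What is at stake is the classification of dysfunction events in the EFS. Section 12.1 has the CEC adjudicate by definitions in the protocol and in its charter, and section 13.0 bases event and endpoint definitions on MVARC, the source named for 17.1.31. An adjudicator who applies the glossary and one who silently substitutes valve area would classify the same echocardiogram differently. A reader looking for the cut-off behind the stenosis endpoint must also go to Appendix 17.1, where two adjacent sections offer different criteria.

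**Working it through.** The plan gives no figure to reproduce here. The check compares the 1.5 cm² cut-off with the CIP's own EROA scale, then with its valve-area criteria.

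**Inputs**
- Cut-off in 17.1.31: 1.5 cm².
- EROA in the 17.1.29 table: mild below 0.20 cm², severe from 0.40 cm².
- Regurgitant volume in the same table: mild below 30 mL, severe from 60 mL.

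**Step 1. Position of the cut-off on the EROA scale**
- Against the severe threshold: 1.5 / 0.40 = 3.75.
- Against the mild limit: 1.5 / 0.20 = 7.5.

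A competent valve (EROA near 0), a mildly leaking valve (below 0.20) and a valve at the severe threshold (0.40) all satisfy EROA < 1.5 cm².

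**Step 2. What it would take to escape the limb**
- Volume per unit area at the severe thresholds: 60 / 0.40 = 150 mL per cm².
- At the mild limits: 30 / 0.20 = 150 mL per cm².
- Scaled to the cut-off: 1.5 × 150 = 225 mL per beat.

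The proportional scaling is my assumption, and the result is only an order of magnitude. It shows that only massive regurgitation would fall outside the limb.

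**Step 3. The *or* conditions**
- The gradient is an alternative to EROA, so a gradient below 5 mm Hg does not clear a valve.
- A valve with EROA of 1.5 cm² or more lies far above the 0.40 cm² severe threshold, so it would meet the residual-MR limb instead.

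Read literally, the whole definition therefore flags essentially every valve.

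**Step 4. Substituting EOA**
- Limb after substitution: EOA < 1.5 cm² **or** gradient ≥ 5 mm Hg.
- Pilot SAP 7.9.2, definition 1 (no stenosis): EOA ≥ 1.5 cm² **and** mean gradient < 5 mmHg.

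These are complements of each other, taking the CIP's transmitral gradient to be the mean gradient. The substituted limb also fits 17.1.30, whose mildest class has valve area above 1.5 cm² and mean gradient below 5 mmHg. The one difference is at exactly 1.5 cm², which 17.1.30 puts in its moderate band and the SAP accepts as no stenosis.

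**The case against.** The strongest reply is that no echocardiographer would be misled. The bracket explains the word stenosis, 17.1.30 immediately before it uses valve area, EFS echo endpoints rest on core-lab assessment (section 5.0), and the CEC charter is meant to set explicit adjudication rules. This largely stands. It is why the literal result should not be taken as a forecast that all subjects will be recorded as dysfunctional. It does not remove the defect: the charter is not among the documents, and a definition should not depend on readers overriding the protocol's own glossary.

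Four stronger readings are tempting and are not supported.

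- *That the EFS defines mitral stenosis through EROA throughout.* It does not; 17.1.30 is free of the term.
- *That an EFS device-success threshold is wrong.* Section 4.2.3 points to Appendix 17.1 for the MVARC outcomes, but that appendix contains no device-success definition. The EROA threshold for device success is in the Pilot CIP only.
- *That Pilot device success would come out near zero.* The Pilot SAP computes it with EOA, so the literal Appendix D rule will not be the one analysed.
- *That Appendix D omits a comparison sign before 1.5 cm².* In the same appendix the intubation, NYHA and six-minute-walk criteria also appear without signs that the SAP prints, so this is probably a text-extraction artefact. The term EROA is not explained that way.

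**Conclusion.** The term in 17.1.31 is wrong as written. On the CIP's own scale the cut-off is 3.75 times the severe-MR threshold, so the stenosis limb has no discriminating value if followed literally. The expected practical effect is smaller: ambiguous or inconsistent classification of dysfunction events. Its frequency cannot be estimated from the documents.

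The primary safety endpoint, related SAEs through 30 days, is not defined by this criterion. Nothing in the text ties the EFS stenosis endpoint to 17.1.31, but nothing rules it out either.

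For the Pilot study the issue is a mismatch of terms between CIP Appendix D and a SAP that already uses the appropriate quantity. That SAP shows what was intended, but it is written for CIP-1403 and does not correct the EFS CIP.

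The conclusion assumes that EROA carries its glossary meaning in 17.1.31; the EFS CIP gives it no other. Whether the term was carried over from the cited consensus document cannot be checked here and does not change the finding.

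**What to change.** 1. In EFS CIP 17.1.31, replace EROA with EOA, so that the limb reads EOA < 1.5 cm² or transmitral gradient ≥ 5 mm Hg.
2. Add EOA (effective orifice area) to the EFS glossary, and keep EROA for the MR table.
3. State whether 17.1.30 or 17.1.31 governs the EFS stenosis endpoint. If 17.1.30 is chosen, also say which of its classes counts as significant.
4. Make the same term correction in Pilot CIP Appendix D so that it agrees with SAP 7.9.2 definition 1 and SAP device success. SAP definition 2 (mean gradient below 10 mmHg alone) has no area component and needs no change for this purpose.
5. Confirm that the CEC charter uses the corrected term, and check that any dysfunction events already adjudicated were read on valve area.

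The cost is a few words in each protocol plus a check of the charter. Version 4.0 of the EFS CIP already amended Section 17 definitions, so this is a routine edit. No new measurement should be needed, because 17.1.30 already calls for valve area.

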### **17.1.32 MORTALITY**

Mortality will be classified according to the Mitral Valve Academic Research Consortium (MVARC); Clinical Trial Design Principles and Endpoint Definitions for Transcatheter Mitral Valve Repair and Replacement: Part 2: Endpoint Definitions; JACC, 2015 (14).

Classification of All-Cause Mortality	
I. Cardiovascular vs. Noncardiovascular Mortality	
A. Cardiovascular Mortality	
Any of the following contributing conditions:	
Heart failure (subclassified into left ventricular vs. right ventricular dysfunction)	Myocardial infarction
Major bleeding	
Thromboembolism	Stroke
Arrhythmia and conduction system disturbance	
Cardiovascular infection and sepsis (e.g., mediastinitis and endocarditis)	Tamponade
Sudden, unexpected death	Other cardiovascular Device failure
Death of unknown cause (adjudicated as cardiovascular)	
B. Noncardiovascular Mortality	
Any death in which the primary cause of death is clearly related to another condition:	
Noncardiovascular infection and sepsis (e.g., pneumonia)	
Renal failure	
Liver failure	
Cancer	
Trauma	
Homicide	
Suicide	
Other noncardiovascular	
II. Periprocedural vs. Nonperiprocedural Mortality	
Death is considered periprocedural if occurring within 30 days of the intervention or beyond 30 days in the patient not yet discharged	

## 17.1.33 MYOCARDIAL INFARCTION

Myocardial infarction (MI) will be defined according to the Mitral Valve Academic Research Consortium (MVARC); Clinical Trial Design Principles and Endpoint Definitions for Transcatheter Mitral Valve Repair and Replacement: Part 2: Endpoint Definitions; JACC, 2015 (14).

Definition of MI After Transcatheter and Surgical Mitral Valve Replacement	
I. Periprocedural MI (<math>\leq 48</math> h after the index procedure)*†	
A.	In patients with normal baseline CK-MB (or cTn): The peak CK-MB measured within 48 h of the procedure rises to $\geq 10$ times the local laboratory ULN plus new ST-segment elevation or depression of $\geq 1$ mm in $\geq 2$ contiguous leads (measured 80 ms after the J-point), or to $\geq 5$ times ULN with new pathological Q waves in $\geq 2$ contiguous leads or new persistent LBBB, OR in the absence of CK-MB measurements and with a normal baseline cTn, a cTn (I or T) level measured within 48 h of the PCI rises to $\geq 70$ times the local laboratory ULN plus new ST-segment elevation or depression of $\geq 1$ mm in $\geq 2$ contiguous leads (measured 80 ms after the J-point), or $\geq 35$ times ULN with new pathological Q waves in $\geq 2$ contiguous leads or new persistent LBBB.
B.	In patients with elevated baseline CK-MB (or cTn): The CK-MB (or cTn) rises by an absolute increment greater than or equal to those levels recommended above from the most recent pre-procedure level plus, new ECG changes as described.
II. Spontaneous MI (<math>>48</math> h after the index procedure)‡	
Detection of rise and/or fall of cardiac biomarkers (preferably cTn) with at least 1 value above the 99th percentile URL (or ULN in the absence of URL) together with at least 1 of the following:	
A.	Symptoms of ischemia
B.	ECG changes indicative of new ischemia (new ST-segment or T-wave changes or new LBBB) or new pathological Q waves in $\geq 2$ contiguous leads
C.	Imaging evidence of a new loss of viable myocardium or new wall motion abnormality
III. MI associated with sudden, unexpected cardiac death‡	
Sudden cardiac death or cardiac arrest, often with symptoms suggestive of myocardial ischemia, and accompanied by presumably new ST-segment elevation or new LBBB and/or evidence of fresh thrombus by coronary angiography and/or at autopsy, but death occurs before blood samples could be obtained or at a time before the appearance of cardiac biomarkers in the blood	
IV. Pathological findings of an acute myocardial infarction‡	
The use of high sensitivity (hs)-troponins is recommended for diagnosis of type II (spontaneous) MI, but has not been studied for assessment of periprocedural MI. Standard troponin assays are therefore recommended for evaluation of type I MI.	
* Periprocedural biomarker elevation $>$ ULN not meeting the criteria for MI should be categorized as "myonecrosis not meeting MI criteria."	
† Adapted from Moussa et al. (43).	
‡ Adapted with permission from Thygesen et al. (39).	
CK-MB = creatine kinase-MB; cTn = cardiac troponin; ECG = electrocardiogram; LBBB = left bundle branch block; MI = myocardial infarction; ULN = upper limit of normal; URL = upper reference limit.	

